**Table 2-1: Screening Procedural Outline (BMS-936558)**

Procedure	Screening Visit a	Notes Enrollment was stopped as of 17-Oct-2019.
Laboratory Tests	X	Complete blood count (CBC) with differential, Chemistry panel including LDH, AST, ALT, ALP, T.Bili, BUN or serum urea level, uric acid, creatinine, Ca, Mg, Na, K, Cl, P, glucose, albumin, amylase, lipase, thyroid stimulating hormone (TSH) (reflex to free T3, free T4 for abnormal TSH result), c-reactive protein ,hepatitis B surface antigen (HBV sAg), and hepatitis C antibody (HCV Ab) or HCV ribonucleic acid (RNA) within 14 days prior to first dose.
Urinalysis	X	Total protein, glucose, blood, leukocyte esterase, specific gravity, and pH, within 14 days prior to first dose.
Pregnancy Test	X	For WOCBP only (serum or urine - local/site)
ECG	X	Within 28 days prior to first dose
Pulmonary Function Test (PFT)	X	Must include testing for diffusing capacity of the lung for carbon monoxide (DLCO). Within 28 days prior to first dose
Efficacy [REDACTED] Assessments		
Radiographic Tumor Assessment FDG PET-CT or PET-MRI scan from vertex to toes	X	Must be performed within 28 days prior to first dose. FDG-PET scan from vertex to toes is required at screening. CT portion of PET-CT must be of diagnostic quality. If low dose CT used, then a separated dedicated CT or MRI of the chest, abdomen and pelvis and other known sites of disease must be acquired.
Collection of tumor tissue	X	Submission of tumor tissue (FFPE tumor tissue block or 25 unstained slides) from a biopsy performed during screening is mandatory. If this is not possible, the following exceptions are allowed:

**Table 2-1: Screening Procedural Outline (BMS-936558)**

Procedure	Screening Visit a	Notes
		
Enrollment was stopped as of 17-Oct-2019.
 
1) Participants who do not have any accessible lesions, or
 
2) Participants who have archival tissue from a previous tumor biopsy [REDACTED]. These participants must submit archival tissue from the most recent tumor biopsy if archival tissues are available from tumor biopsies at multiple timepoints. While submission of archival tissue from the most recent tumor biopsy is mandatory, archival tissue from other tumor biopsy is strongly encouraged. For example, participants who mandatorily submit archival tissue from a tumor biopsy at relapse may optionally submit archival tissue for tumor biopsy at initial diagnosis.
 
[REDACTED]
 
Biopsy samples should be excisional, incisional, or core needle. Tumor biopsies (FFPE) for IHC of tumor and TIL and RNALater for gene expression.

IVRS/Clinical Drug Supplies		
Phone calls to IVRS/Randomize	X	
Phone calls must be made to IVRS as follows:
 
For subject number assignment at the time informed consent is obtained and trigger 1st shipment of drug.

a Within 28 days prior to first dose

**Table 2-2: Procedural Outline During the Treatment Period (CA209812)**

Procedure	Cycle 1 Day 1 - Disease Progression or Unacceptable Toxicity	Notes  All windows proposed are calendar days. Procedures must be done within 72h prior to dosing unless otherwise specified. Dosing is to be performed every 3 weeks
Safety Assessments		
Targeted Physical Examination	X	Lymph node areas (for example, but not limited to, submandibular, cervical, supraclavicular, axillary, or inguinal lymph node), and abdominal organs (eg, spleen, liver)
Vital Signs	X	Includes body temperature, respiratory rate (RR), and seated blood pressure (BP) and heart rate.
Physical Measurements	X	Within 72 hours prior to dosing. Includes Weight and ECOG performance status ( Appendix 7 )
Adverse Events Assessment	Continuously	See Appendix 2/Section 9.2 . Assessed using NCI CTCAE v. 4.03.
Serious Adverse Events Assessment	Continuously	See Appendix 2/Section 9.2 . Assessed using NCI CTCAE v. 4.03
Review of Concomitant Medications	X	See section 7.7
Laboratory Tests	X	Within 72 hours prior to dosing to include CBC w/differential, AST, ALT, ALP, TBili, BUN or serum urea level, creatinine, Ca, Mg, Na, K, Cl, phosphate, LDH, glucose, amylase, lipase, c-reactive protein, albumin
Thyroid Function Testing	See note	TSH (reflex to free T3 and free T4 if abnormal result) to be performed every 9 weeks ( $\pm$ 7 days) from first dose regardless of dosing schedule.
Pregnancy Test for WOCBP	X See note	Serum or urine within 24 hours prior to first dose and then at least once every 4 weeks ( $\pm$ 7 days) regardless of dosing schedule.
Efficacy Assessments		
Radiographic Tumor Assessment FDG-PET-CT or PET-MRI scans from vertex to toes	See note	FDG PET-CT or PET-MRI will be performed at the end of cycle 5, 10, 15, and every 5 cycles until disease progression. FDG PET-CT or PET-MRI can be performed as clinically warranted for suspicion of recurrence during the non-protocol specified time points
B symptoms	See note	Collected Day 1 (prior to dosing) of every other cycle (cycle 1, 3, etc)

**Table 2-2: Procedural Outline During the Treatment Period (CA209812)**

Procedure	Cycle 1 Day 1 - Disease Progression or Unacceptable Toxicity	Notes  All windows proposed are calendar days. Procedures must be done within 72h prior to dosing unless otherwise specified. Dosing is to be performed every 3 weeks
Clinical Drug Supplies		
Administer Study Drug	X	IVRS should be called within 3 days prior to study treatment administration to receive vial assignment.

**Table 2-3: Procedural Outline after the Treatment Period (CA209812) - Follow Up**

Procedure	X, Follow-Up, Visits 1 and 2 a	Notes
Safety Assessments		
Targeted Physical Examination	X	Lymph node areas (for example, but not limited to, submandibular, cervical, supraclavicular, axillary, or inguinal lymph node), and abdominal organs (eg, spleen, liver)
Serious Adverse Events Assessment	X	SAEs related to any later protocol-specified procedure must be collected
Adverse Events Assessment	X	Non-serious AEs and SAEs must be collected up to 100 days after study treatment discontinuation.
Peripheral Neuropathy	X	Any AEs of peripheral neuropathy must be followed until resolution or end of study, whichever occurs first.
Monitoring for (in)fertility	X	Completion of CRF through Safety Follow-up Visit 2.
Monitoring for cardiotoxicity and pulmonary toxicities	X	Completion of CRF through Safety Follow-up Visit 2 and work up as indicated (for clinical symptoms)
Monitoring for secondary neoplasms	X	Completion of CRF through Safety Follow-up Visit 2.
Laboratory Tests	X	During Follow-up visit 1 and Follow-up visit 2: CBC with differential, BUN or serum urea level, serum creatinine, sodium, potassium, calcium, magnesium, chloride, glucose, AST, ALT, total bilirubin, alkaline phosphatase, LDH.
Thyroid Function Testing	X	TSH (reflex to free T3 and free T4 if abnormal result) Every 9 weeks
Pregnancy Test (WOCBP only)	X	Serum or urine (WOCBP only)

**Table 2-3: Procedural Outline after the Treatment Period (CA209812) - Follow Up**

Procedure	X, Follow-Up, Visits 1 and 2 a	Notes
Efficacy Assessments		
B Symptoms	X	To be collected only at Follow-up Visit 1
Radiographic Assessments		
FDG-PET CT or FDG MRI scan from vertex to toes b	See note	For participants who discontinue study treatment prior to disease progression, no further FDG-PET CT or PET MRI will be obtained.
Participant Status		
Survival Status	X	Survival follow-up will stop after safety Follow-up Visit 2.

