**Overall Design:**

This is a 1:1 randomized, open-label phase 3 study in advanced cHL participants  $\geq 18$  years old who are relapsed refractory or ineligible for autologous stem cell transplant (ASCT). Patients will be balanced in the 2 groups in regards to prior therapies. Approximately 340 participants will be treated in one of two arms: 1) nivolumab 360 mg IV every 3 weeks until progression or unacceptable toxicity (except for patients in CR who can discontinue at 2 years) plus BV 1.8 mg/kg IV every 3 weeks for 16 cycles, or until progression or unacceptable toxicity, whichever occurs first or 2) BV alone 1.8 mg/kg every 3 weeks for 16 cycles, or until progression or unacceptable toxicity, whichever occurs first. Treatment may also be discontinued if the participant meets other criteria for discontinuation of study drug outlined in [Section 8.1](#) of the protocol. Participants receiving nivolumab who achieve CR may discontinue treatment after a maximum of 2 years of therapy, provided that there is no prohibitive toxicity. Participants can be BV- naïve, or can have prior BV treatment as a single agent or in combination in any line of therapy. Randomization stratification will be performed on the following two factors: 1) Prior ASCT status (YES/NO). 2) Prior BV use (YES/NO). Participants will be balanced based on the stratification factors per arm.

Participants will undergo screening evaluations to determine eligibility within 28 days prior to first dose. Each 21-day dosing period will constitute a cycle.

Study visits and endpoint measurements will occur as indicated in [Table 2-1](#) though [Table 2-3](#) in the protocol.

Any participant who discontinues the study treatment prior to progression will be followed for progression, then survival, in the follow up phase of the study.

[figure not shown]
As of 17-Oct-2019, enrollment in this study was stopped at the decision of the Sponsor. For currently enrolled participants, at the investigator's discretion, the same study treatment can be continued if the participant is considered to have clinical benefit. Assessments of efficacy and safety will continue per protocol; however, efficacy assessments will be done by investigator.

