For participants who continue the study treatment, BMS will continue to provide study drugs, per country requirements, until the participant meets the protocol discontinuation criteria. Participants who discontinue all study drugs will continue safety follow-up per protocol requirements. Survival follow-up will stop at safety follow-up visit 2 as presented in the Schedule of Activities.

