**Table 2-3: Procedural Outline after the Treatment Period (CA209812) - Follow Up**

Procedure	X, Follow-Up, Visits 1 and 2 a	Notes
Subsequent anti-lymphoma therapies	X	It can be accomplished by visit or phone contact to assess subsequent anti-cancer therapy. Per Revised Protocol 01, stop after safety Follow-up Visit 2.
Post-nivolumab stem cell transplant follow-up (if applicable)	X	Completion of associated eCRF page. Per Revised Protocol 01, stop after safety Follow-up Visit 2.
GVHD Assessments	X	Only for participants who discontinued study therapy by proceeding to allogeneic SCT. See Section 9 and Appendix 9 . Per Revised Protocol 01, stop after safety Follow-up Visit 2.

a X, Follow-up visit 01 occurs 35 days ± 7 days from last dose and Follow-up visit 02 occurs 100 days ± 7 days from the last dose.

b Should a participant have a contraindication for CT IV contrast, a non-contrast CT of the chest and a contrast enhanced MRI of the abdomen and pelvis may be obtained. CTs and MRIs should be acquired with a slice thickness of 5 mm or less with no gap (contiguous).

[figure not shown]

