**Figure 5.1-1: Study Design Schematic**

Abbreviations: BV = brentuximab vedotin; PFS = progression-free survival; CRR = complete response rate; OS overall survival; ORR = objective response rate; DOCR = duration of complete response; DOR = duration of response.

This is a 1:1 randomized, open-label Phase 3 study in advanced cHL participants ≥ 18 years old who are relapsed refractory or ineligible for ASCT. Patients will be balanced in the 2 groups in regards to prior therapies. Approximately 340 participants will be treated in one of 2 arms. In one arm, participants will receive nivolumab 360 mg IV every 3 weeks until progression or unacceptable toxicity (except for patients in CR who can discontinue at 2 years) plus BV 1.8 mg/kg IV every 3 weeks for up to 16 cycles, or until disease progression or unacceptable toxicity,

whichever occurs first. In the other arm, participants will receive BV alone 1.8 mg/kg every 3 weeks for up to 16 cycles, disease progression, or unacceptable toxicity, whichever occurs first. Discontinuation of study therapy can also occur if the participant meets other criteria outlined in [Section 8.1](#). Participants receiving nivolumab who achieve CR may discontinue treatment after a maximum of 2 years of therapy, provided that there is no prohibitive toxicity. Participants can be brentuximab vedotin-naïve, or can have prior BV treatment as a single agent or in combination in any line of therapy. Randomization stratification will be performed on the following two factors: 1) Prior ASCT status (YES/NO). 2) Prior BV use (YES/NO). Participants will be balanced based on the stratification factors per arm. The two arms will be balanced in regards to these stratification factors.

Participants will undergo screening evaluations to determine eligibility within 28 days prior to first dose. Each 21-day dosing period will constitute a cycle.

Study visits and endpoint measurements will occur as indicated in [Table 2-1](#) through [Table 2-3](#).

Any participant who discontinues the study treatment prior to progression will be followed for progression, then survival, in the follow up phase of the study.

- No dose reductions or escalations of nivolumab are permitted. Skipped doses will not be made up. For dose modifications or reductions of BV, see [Section 7.4.2](#).

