- Duration of study participation: Randomization is within 28 days of the screening. The recruitment period is approximately 34 months with a follow up of 4 years after the last patient first visit (LPFV). Participants will receive active treatment of nivolumab until progression or unacceptable toxicity plus BV for 16 cycles or until progression or unacceptable toxicity, whichever comes first, or BV alone up to 16 cycles, or until progression or unacceptable toxicity, whichever occurs first. The treatment period will be followed by a survival follow up period.

As of 17- Oct- 2019, enrollment in this study was stopped at the decision of the Sponsor. For currently enrolled participants, at the investigator's discretion, the same study treatment can be continued if the participant is considered to have clinical benefit. Assessments of efficacy and safety will continue per protocol; however, efficacy assessments will be done by investigator. [REDACTED]

[REDACTED] For participants who continue the study treatment, BMS will continue to provide study drugs, per country requirements, until the participant meets the protocol discontinuation criteria. Participants who discontinue all study drugs will continue safety follow-up per protocol requirements. Survival follow-up will stop at safety Follow-up Visit 2 as presented in [Table 2-3](#).

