### **8.1.1 Post Study Treatment Study Follow-up**

In this study, PFS is a key endpoint of the study. Post study follow-up is of critical importance and is essential to preserving participant safety and the integrity of the study. Participants who discontinue study treatment must continue to be followed in line with [Section 2](#) through Safety Follow-up Visit 2. Study objectives and endpoints are listed in [Table 4-1](#).

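### Scheduled control-arm imaging nominally ends at 10.3 months under Revised Protocol 01, yet 12- to 24-month PFS rates stay in the plan with no condition tied to imaging

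*Protocol*

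**What the plan says.** **Imaging after treatment.** The radiographic row of Protocol Table 2-3 reads: "For participants who discontinue study treatment prior to disease progression, no further FDG-PET CT or PET MRI will be obtained." The Synopsis (Overall Design) says: "Any participant who discontinues the study treatment prior to progression will be followed for progression, then survival." Section 5.1 repeats this: a participant who "discontinues the study treatment prior to progression will be followed for progression, then survival." Section 8.1.1 states "In this study, PFS is a key endpoint of the study" and refers post-treatment follow-up to Section 2, through Follow-up Visit 2.

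**Imaging and survival contact otherwise.** Table 2-2: "FDG PET-CT or PET-MRI will be performed at the end of cycle 5, 10, 15, and every 5 cycles until disease progression." It also permits unscheduled scans when recurrence is suspected. Section 7.1 caps BV at 16 cycles. Nivolumab runs until progression or unacceptable toxicity, and participants in CR may stop at 2 years. The Synopsis says: "Survival follow-up will stop at safety follow-up visit 2 as presented in the Schedule of Activities." Table 2-3, footnote a, adds: "Follow-up visit 02 occurs 100 days ± 7 days from the last dose."

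**Analyses.** Protocol Section 10 rules out formal testing and inference, records 23 randomized participants, allows the earlier planned analyses only where appropriate, and refers to the SAP for detail. Section 10.3.1 still lists Kaplan-Meier PFS rates per arm at 6, 12, 18 and 24 months. SAP 7.5.1 allows PFS rates at 12, 18, 24 and 36 months once minimum follow-up reaches the timepoint. SAP 7.5.2.3 applies the same condition to OS rates from 6 to 36 months. SAP 7.5.3.1 defines minimum follow-up as last randomization to clinical cutoff. The SAP is version 1.0 of 24-Feb-17 and lists no amendments. Protocol 10.3 expects it to be finalized before database lock.

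**The concern.** Two statements in the current protocol cannot both be followed: one ends scans when treatment stops without progression, the other promises follow-up for progression. If Table 2-3 is applied, length of imaging depends on length of treatment. That differs by arm by design, because BV has a fixed cap and nivolumab does not.

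The landmark rates were not adjusted to match. Event-free participants are censored at their last tumor assessment (Protocol 10.3.1, SAP 4.1), whereas a later death without progression or subsequent therapy counts on its own date. Beyond the last control-arm scan, the control participants still in the risk set are therefore mainly those who go on to die. A control-arm rate at 12 months or later could appear beside a nivolumab-arm rate that rests on scans, and a reader could not tell the two apart.

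**Working it through.** **Inputs.** Cycle = 21 days (Protocol 5.1). BV maximum = 16 cycles (7.1). Scans at the end of cycles 5, 10, 15 and every 5 thereafter (Table 2-2). Visit 2 = last dose + 100 days (Table 2-3). 1 month = 30.4375 days (SAP 8).

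**The plan's own figure.** Protocol 5.5.1 equates 16 BV cycles with about one year: 16 × 21 = 336 days; 336 / 365.25 = 0.92 year. This agrees.

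**End of scheduled control-arm observation, no delays.**
- Scans: 5 × 21 = 105, 10 × 21 = 210 and 15 × 21 = 315 days, or 3.45, 6.90 and 10.35 months from first dose. No scan is scheduled at the end of treatment.
- The cycle-16 dose is given on day 315, so Visit 2 is at 315 + 100 = 415 days = 13.6 months.
- Nivolumab-arm scans on treatment continue at 420, 525, 630 and 735 days = 13.80, 17.25, 20.70 and 24.15 months.

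| Landmark | Days | Days after last control scan (315) | Days after Visit 2 (415) |
|---|---|---|---|
| 12 months | 365.25 | 50 | reached |
| 18 months | 547.9 | 233 | 133 |
| 24 months | 730.5 | 416 | 316 |
| 36 months | 1095.75 | 781 | 681 |

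**Can the SAP condition be met regardless?** Assume cutoff at end of trial, when all participants have passed Visit 2 (Protocol 5.3).
- If the last participant randomized is a control who completes 16 cycles, cutoff is at least 415 days after last randomization. Since 415 > 365.25, the 12-month condition is met, although that participant's scheduled scans ended at day 315.
- One nivolumab participant treated for 2 years keeps the trial open to 730 + 100 = 830 days from that participant's start. The condition is met if the start was no more than 830 − 365.25 = 465 days (15.3 months) before last randomization for the 12-month rate, 830 − 547.9 = 282 days (9.3 months) for 18 months, or 830 − 730.5 = 99.5 days (3.3 months) for 24 months.
- For 36 months, 830 < 1095.75, so this scenario cannot meet the condition. Even if that participant were the last randomized, it would take 1095.75 − 100 ≈ 996 days of treatment, or 32.7 months.

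**Effect on the estimate.** If all event-free controls are censored by day 315 and none dies later, the Kaplan-Meier estimate is undefined beyond that day. A death with *k* at risk multiplies the estimate by 1 − 1/*k*: 0, 0.50 and 0.67 for *k* = 1, 2 and 3. On the nominal schedule a single later death occurs with *k* = 1, and the curve drops to 0.

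**Data from before the revision.** For 12, 18 or 24 months to have passed by the revision date (08-Jan-2020), a control had to be randomized by about 08-Jan-2019, 09-Jul-2018 or 08-Jan-2018. From the original protocol (22-Feb-2017) to the revision is 1050 days = 34.5 months, so 36 months could not have been reached by then.

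**The case against.** The strongest reply is that nothing obliges the sponsor to report a late rate. Section 10 makes the planned analyses conditional, Section 10.3 introduces 10.3.1 as a summary, and the SAP only permits the later rates. This is correct: a reader might infer that the plan mandates a 24-month control-arm rate, and it does not. But neither clause states a criterion, and the only one to be found is the calendar condition.

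Second, the SAP predates the revision, so the mismatch is one symptom of a SAP not yet updated. That is also true, and the update is where the repair belongs. However, Section 10.3.1 was itself revised to investigator assessment and kept the landmarks.

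Third, 10.3 months is not a hard limit. BV delays are allowed; about 50 cumulative days (365.25 − 315) would move the cycle-15 scan to 12 months. Unscheduled scans and imaging done before the revision may also reach further. All of this stands, and a rule based on the data actually collected allows for it.

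Fourth, the distortion needs a particular event. For a control completing 16 cycles on the nominal schedule, the death must fall between day 315 and about day 415, and within the first 50 of those days to lower the 12-month rate. A step of 0.50 or 0.67 needs further controls still at risk. So the harm is possible rather than expected. An undefined estimate is the more ordinary result, and the plan does not say how to report that either.

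Fifth, the promise to follow for progression may be leftover text, since Section 8.1.1 refers to Section 2. It nevertheless stands unqualified in two places. The 4-year follow-up wording in Section 5.1 ("The recruitment period is approximately 34 months with a follow up of 4 years after the last patient first visit (LPFV)") is different: the later paragraph of that section and Section 5.3 override it. It does not show that long survival follow-up is still planned.

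**Conclusion.** The point holds as a minor to modest matter of consistency and reporting. The imaging passages conflict. On the nominal schedule, scheduled control-arm scans stop 50, 233 and 416 days before the 12-, 18- and 24-month landmarks. The only stated condition on late rates can be met without any control participant imaged that far.

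This assumes no delays, no unscheduled scans and no longer pre-revision data. The condition's behaviour also assumes cutoff at end of trial. The arm split and individual dates of the 23 participants are not given, so how many controls have longer imaging is unknown.

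Three stronger readings are not supported. Unequal imaging does not compromise a formal PFS comparison, because none will be made. The 36-month rate is secondary, since its condition would need nivolumab treatment well beyond 2 years. OS landmark rates appear only in the 2017 SAP; the current protocol plans OS curves and medians, and Visit 2 does reach 12 months for participants who complete 16 cycles without delay.

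**What to change.** Make these changes with the SAP update due before database lock.

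1. Reconcile the Synopsis and Section 5.1 statements on follow-up for progression with Table 2-3.
2. Add a condition to Protocol 10.3.1, which has none of its own, and replace the calendar condition in SAP 7.5.1 and 7.5.2.3 with a per-arm rule. Report a PFS landmark rate only if tumor assessments in that arm reach the timepoint, and an OS rate only if survival follow-up in that arm does. Also report the rate if the Kaplan-Meier estimate has already reached 0 through documented events within the arm's observed assessment period. Otherwise report it as not estimable. The exception matters: if every control has progressed on scans, 0% is a real result and must not be suppressed. Judging arms separately keeps valid nivolumab-arm rates and any longer control data.
3. Show numbers at risk by arm, and state that imaging duration follows treatment duration and so differs by arm. Optionally, add a supportive PFS analysis truncated in both arms at the end-of-cycle-15 scan.

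Items 2 and 3 need wording and tables only, with no extra scans or visits. Item 1 is also wording only, provided the reconciled text adds no imaging. The price is fewer late descriptive rates.
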